learning paradigm^{39,70}. This learning task is essentially a more difficult version of the Wisconsin Card Sorting task. More specifically, participants must dynamically learn different categories of stimuli as well as the exceptions. Participants receive feedback (correct/incorrect) on each trial to shape learning. Intermittently, and disproportionately on incorrect trials to increase stress, participants are instructed to increase performance speed. Additionally, trials are embedded in counterbalanced blocks of threat of unpredictable shock. Half of the blocks are “No Shock” probability blocks, whereas half of the blocks are “Unpredictable Threat of Shock.” Thus, in addition to performance demands participants must contend with a psychologically threatening and unpredictable context during performance. Typically, more efficient learning and performance is predicted by increased midline theta oscillations (4-8 Hz) and increased intersite phase synchrony during feedback, and further enhanced under threat or stress among those with successful performance³⁹. Responses to blocks of unpredictable threat and no threat will be compared in terms of autonomic measures (heart rate and skin conductance) as well as the responses to 50 ms, 98 dB white noise probes, which elicit a blink response (i.e., startle reflex) measured with electromyography (EMG). The reactions captured in these measures reliably increase as a function of stress and aversion as well as lack of resilience⁷¹⁻⁷⁴. In summary, we predict that EEG metrics of cognitive control will be enhanced pre- to post-treatment as a function of dose, and more pronounced under threat, indicative of enhanced cognitive control and resilience. We predict that concurrent physiological metrics of stress reactivity during unpredictable relative to no threat of shock will be reduced pre- to post-treatment, more so at higher doses, indicative of improved resilience. Shock level will be individually titrated prior to the learning procedure. EEG will be assessed pre- and immediately post-treatment as well as 1 month later (64-channel Brain Products ActiChamp System). Startle, heart rate and skin conductance will be assessed with Biopac EMG, EKG, and EDA modules.

10.0 Data Management

Confidentiality. Any discussion of identifying sensitive information will occur in private rooms at the Brain Stimulation Laboratory, [name] Center for Biomedical Imaging, or the Department of Radiology. Regarding documentation, participants’ names will appear only on the IRB-approved Consent, HIPAA, and payment forms, initial screening form, and in a separate key file that links individual participant names and contact information to a random participant identification code. The participant identification code will be assigned to the individual during Visit 1 and all subsequent data collection will reference this code. The key linking individual identifying information to the participation code will be maintained in an electronic database accessible only to the PI and her designees in a password-protected file on an encrypted and password protected network (MUSC LAN). The questionnaire data collected through RedCap will be referenced by participant ID only and collected via a HIPAA compliant interface and downloaded to the MUSC server once a participant has completed participation. If a participant consents to participate at the interview, the initial screening form will be entered into a secure electronic database according to the assigned participation code and then locked in the PI’s office, separate from payment and consent forms including health information. If a participant declines consent or is lost to follow-up (i.e., defined as not appearing for intake within 1 month of screen), the screening form will be securely shredded. The consent, HIPAA, and payment forms will be kept in a locked cabinet in the PI’s locked office. All other collected paper (e.g., interview responses) and electronic (e.g., questionnaire, neurocognitive, MRI data) files will be identifiable only by participant code and stored in locked file cabinets or on the secure MUSC LAN at the Institute of Psychiatry (non-MRI

data) and Center for Biomedical Imaging (MRI data). The key file linking names to IDs will be deleted after data collection is complete.

Consent and HIPAA forms will be kept on file for 6 years. Contact information is kept on file for 6 years if the participant consents to allowing their information to remain active in our files, or the contact information is destroyed immediately after the study is completed if participants chose that option on the consent form. Although individual-subject analyses may be written up in publications, the individual subjects producing that data will never be identified by name or initials, or any other identifying information.

All study personnel will complete all annual MUSC CITI training concerning confidentiality and research ethics.

The PI will monitor data quality on a weekly basis to ensure integrity, completeness, and fidelity to the IRB protocol.

Statistical Plan.

Arms 1 and 4. Dose-response relationships for the primary and secondary efficacy endpoints of change in neurocognitive performance (composite measure), EEG, and resilience, stress and symptoms would be assessed using the multiple comparisons procedure with modeling (MCP-Mod) approach for 1 and 2 month outcomes. To determine the reliability of a dose response, MCP-Mod fits a set of pre-specified candidate dose-response curves to the data using a multiple-comparisons technique. The pre-specified dose-response curves to be tested for resilience and neurocognitive performance would be Emax, logistic, and linear. Significant curves would then be used to develop inferences on optimal doses for the randomized controlled trial in aim 2. Descriptive statistics would be performed on acceptability ratings, adverse events, and dropout rates. Linear mixed- effects models would assess the trajectory of pain/discomfort ratings.

The rationale for participant/dose ratio. Dose-response studies are not powered in the traditional manner. In order to resolve the shape of the continuous dose response function, it is statistically more efficient to select more doses as opposed to more participants^{57,58}. The number of observations within each dose is primarily to account for sampling variability, which could be achieved with a minimum of 2 to 3 observations. Capturing variability is essential to the planned analyses, which underweight the points of greatest variability in estimating the response curve. To contend with dropout we propose to enroll 60, with the aim of completing assessments and treatment for 50 participants. We conservatively expect an 80-90% retention rate, as dropout is typically fewer than 10% in double-blind trials of conventional daily⁵⁹ as well as accelerated rTMS³¹.

Arm 2. Descriptive statistics would be performed on acceptability ratings, adverse events, and dropout rates. Linear mixed-effects models would assess group x pre/post rTMS change in neurocognitive performance, resilience and stress self-report measures, and EEG and ERP metrics. Regarding statistical power, we based predicted effect sizes on findings of neurocognitive enhancement by Holtzheimer et al.³¹ in an accelerated rTMS protocol, specifically, reliable change of 5 standard units on the RBANS (SD=8.9). Specifically, group sample sizes of 27 achieve 80% power to detect a difference of 5.000 (SD=8.9) in a design with 3 repeated measurements having a Compound Symmetry covariance structure, the correlation between observations on the same subject is 0.300, and alpha level is 0.050. We propose to enroll 70 people to contend with dropout with target completion reached with 30 participants each completing active and sham conditions (60 participants total).

Arm 3. A power analysis was performed to determine the number of subjects needed to study physiological effects of simulated microgravity on motor threshold determination. With our study design, each subject will be his/her own control. For calculation of the study's power, we used data of Wassermann⁵⁴ who examined session-to session variability of motor threshold in 19 subjects on three separate occasions and computed the average coefficient of variation in motor threshold across sessions as 0.058 ± 0.036 . Based on this data, a total of 10 subjects will have a 99% chance (at a two sided 5% significance level) to detect a change in motor threshold due to an experimental intervention (parabolic flight) with an effect size of 1.61.

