7	Neurocognitive Battery Questionnaire Battery	MUSC Brain Stimulation Laboratory in the Institute of Psychiatry	90 minutes 1 hour
8	1 month post-treatment Neurocognitive Battery	MUSC Brain Stimulation Laboratory in the Institute of Psychiatry	90 minutes 1 hour

1 month post-treatment Questionnaire Battery		
---	--	--

*Option to complete remotely due to COVID-19 precautions.

Study Arm 2: Efficacy & Safety

Assessment & rTMS. The assessment and TMS methods from study 1 will be identical, except that 60 participants (enrollment n=70 to complete assessments and treatment for n=60 to contend with drop out) will be randomized to one dose of active or sham iTBS rTMS. **The dose will be determined as the most efficacious dose from Study 1, minimizing side effects and burden.** In addition, to determine longer-term safety of the intervention, participants will complete neurocognitive, resilience and symptom measures pre- and immediately post-treatment as well as 1, 2, and 6 months later.

MRI assessment. To more specifically examine safety, participants who received active stimulation will undergo MRI sessions (FLAIR, diffusion, T2* and volumetric sequences) for assessment of structural changes at pre- and post-treatment, and 6 months later.

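### If Arm 2 is run, its group x pre/post model, as conventionally fitted, leaves the randomised baseline largely unused; baseline adjustment would raise power from 55% to about 81% with two post-treatment visits under the plan's own inputs.

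*Combined protocol and SAP*

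**What the plan says.** Section 10.0, Statistical Plan, Arm 2, gives the whole efficacy model in one sentence: "Linear mixed-effects models would assess group x pre/post rTMS change in neurocognitive performance", with the resilience, stress, EEG and ERP outcomes treated the same way. Neither this sentence nor any other part of the document says how the baseline score enters.

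The same paragraph holds the sample-size statement: "group sample sizes of 27 achieve 80% power" for a difference of 5.000 with SD 8.9, "in a design with 3 repeated measurements having a Compound Symmetry covariance structure", where "the correlation between observations on the same subject is 0.300, and alpha level is 0.050". The target is 30 completers each on active and sham.

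Section 9.0 (Study Arm 2) randomises participants to active or sham and states that "participants will complete neurocognitive, resilience and symptom measures pre- and immediately post-treatment as well as 1, 2, and 6 months later". Table 3, which covers Arms 2 and 4, shows the neurocognitive battery at baseline, after treatment and at 1 month only. Section 3.0 makes neurocognitive performance the primary outcome. Sections 2.0 and 5.0 say that studies 1 and 2 were combined into Arm 4, yet Arm 2 keeps its own sample size, methods and analysis.

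**The concern.** Randomisation makes the active and sham baseline means equal in expectation. A group x pre/post model with a free baseline mean per group ignores this and estimates the two means separately. With complete data its interaction term is the difference in raw change scores, so all of the baseline noise is subtracted into the outcome. When baseline and follow-up correlate at only 0.30, that subtraction adds more noise than it removes. At stake is the power of the primary sham-controlled test, and also whether the 80% quoted in the plan belongs to that test.

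**Working it through.** **Inputs** (Section 10.0, Arm 2, unless noted): difference d = 5; SD = 8.9, taken as the per-visit SD; compound symmetry with rho = 0.30; 3 measurements; 30 completers per group. Alpha is 0.05; sidedness is not stated for Arm 2, and two-sided is assumed. Post-treatment visits: k = 2 in Table 3; k = 1 if pre/post is read literally; k = 4 in the Section 9.0 text.

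**Step 1: the plan's own figure.** The variance of a mean over 3 measurements is SD² x (1 + 2 x 0.30)/3 = 0.533 SD² = 42.2. Then n = 2 x (1.960 + 0.842)² x 42.2/25 = 26.5, so 27 per group. Power at 27 is 80.7% (normal approximation) or 79.2% (noncentral t). The stated figure therefore reproduces, but for a group difference averaged over all three measurements, baseline included. Other readings do not give 27: one-sided 21; a single measurement 50; change from baseline 53 with two post-treatment visits or 70 with one.

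**Step 2: variance per participant, in units of SD².**
- Mean of k post-treatment visits minus baseline: (1 + (k-1)rho)/k + 1 - 2 rho.
- Baseline-adjusted: (1 + (k-1)rho)/k - rho².
- The excess of the first over the second is (1 - rho)² for any k, which is never negative. At rho = 0.30 it is 0.49.

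For k = 1: 1 + 1 - 0.60 = 1.40 against 1 - 0.09 = 0.91. For k = 2: 0.65 + 1 - 0.60 = 1.05 against 0.65 - 0.09 = 0.56.

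**Step 3: power at 30 per group.** The standard error is 8.9 x sqrt(2v/30). Power is from the noncentral t with 58 df (change) or 57 df (adjusted). The n for 80% uses the normal approximation.

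| Post-treatment visits | Analysis | v | SE | Power | n per group for 80% |
|---|---|---|---|---|---|
| 1 | change | 1.40 | 2.719 | 44.0% | 70 |
| 1 | adjusted | 0.91 | 2.192 | 61.1% | 46 |
| 2 | change | 1.05 | 2.355 | 55.1% | 53 |
| 2 | adjusted | 0.56 | 1.720 | 81.5% | 28 |

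A simulation of 40,000 trials, which allows for chance baseline imbalance, gives 43.9% and 60.7% (one visit) and 54.9% and 80.7% (two visits); hence about 81% for the last row. A longitudinal model with the baseline mean constrained equal has the same standard errors as the adjusted rows. At 27 per group the two-visit figures are 50.7% and 77.2%.

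**Step 4: sensitivity** (30 per group).
- rho = 0.5 (assumption): 57.1% to 69.5% with one visit, 69.5% to 85.7% with two; gains of 12 and 16 points.
- rho = 0.7 (assumption): 78.9% to 85.0% with one visit, 89.1% to 94.6% with two; gains of about 6 points.
- Four post-treatment visits at rho = 0.30: 62.8% to about 93%.
- If 8.9 were the SD of change instead (rho = 0.30): 57.1% to 75.6% with one visit, 69.5% to 92.2% with two.

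**The case against.** **Arm 2 may not run.** The sponsor approved merging studies 1 and 2 into Arm 4, which has no sham-only group and is analysed by MCP-Mod. This stands, and it makes the point conditional. It does not remove it, because the Arm 2 target, methods and analysis are still in the current text.

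**The model is not written out.** A mixed model with a common baseline mean would also fit the plan's sentence. This stands too: a free baseline effect is the conventional reading, not a stated one. It is a reason to specify the model.

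**The size rests on rho = 0.30.** That value is a planning input for a different contrast, and nothing in the documents shows that it describes the neurocognitive composite. A reader might infer that the test always loses a third to nearly half of its information. That holds only at rho = 0.30 (0.49/1.40 = 35%; 0.49/1.05 = 47%). At rho = 0.7 the loss is 0.09/0.60 = 15% or 0.09/0.45 = 20%.

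**This is efficiency, not validity.** A reader might infer that the planned test is biased or has the wrong type I error. It does not: under randomisation the change-score comparison is unbiased, and it matches the prediction in Section 9.0 of pre-to-post change in active relative to sham. The adjusted analysis, however, estimates the same treatment effect more precisely.

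**SD and visits are uncertain.** The plan attaches 8.9 to a reliable change on the RBANS, so it could be read as the SD of change. The 27 per group reproduces with 8.9 as the per-visit SD. The text and Table 3 also disagree on visits. Both affect the figures but not the direction.

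**Conclusion.** The point holds as a conditional matter of efficiency. If Arm 2 is run with separate baseline means, the group x pre/post test has 44% power with one post-treatment visit or 55% with two. Baseline adjustment gives 61% or about 81%. These figures rest on SD 8.9 per visit, rho 0.30, 30 completers per group and a two-sided 5% test. The gain shrinks as rho rises. Whatever rho is, adjustment costs no more than one degree of freedom.

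Two limits matter. With a single post-treatment visit, power stays well below 80% even after adjustment, so the visits in the contrast must be named. And the plan's 80% at 27 per group describes a contrast that includes the pre-treatment visit, so it should not be quoted for the pre/post test.

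**What to change.** In Section 10.0, Statistical Plan, Arm 2:

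1. Replace the interaction test with a linear mixed model of the post-treatment scores on group, visit, group x visit and baseline score. A longitudinal model with the baseline mean constrained equal in both groups is an equivalent alternative.
2. Define the test as the active-minus-sham difference averaged over the immediate post-treatment and 1-month visits. This matches Table 3 and the three repeated measurements in the power statement. Reconcile the Section 9.0 schedule with Table 3.
3. Use the same form for the resilience, stress and EEG/ERP outcomes.
4. Restate power for this contrast: about 77% at 27 per group and about 81% at 30, two-sided 5%. Say whether 8.9 is a per-visit SD, and show the result for other values of rho.
5. State whether Arm 2 is still to be run. If not, remove its analysis text.

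The cost is a few sentences and one degree of freedom. Baseline is already collected, and no extra participants or visits are needed.

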The left dIPFC site typically targeted with rTMS is seated in an area of cortex integral to intact higher order cognition (i.e., executive function)²³. Co-I [name] has demonstrated that this left dIPFC region (as well as the rest of the cognitive control or multiple demand network) is commonly hypoactivated during cognitive tasks across neuropsychiatric disorders. This was observed in a transdiagnostic functional neuroimaging meta-analysis of more than 11,000 neuropsychiatric patients and matched control participants (Figure 1)²⁴. Furthermore, we have observed during functional magnetic resonance imaging (fMRI) concurrent with TMS, that TMS pulses to the left dIPFC cause BOLD activation in distributed regions of the cognitive control or multiple demand network (Figure 2; Badran et al., in preparation).

Even among healthy individuals for whom neurocognitive performance has a more restricted range, improved working memory performance has been observed after only a single session of excitatory rTMS^{25,26}. Regarding neurocircuit based effects, multiple sessions (i.e., 2 weeks) of excitatory rTMS to left dIPFC among a separate sample of healthy participants have been shown to enhance the efficiency of the cognitive control network during working memory performance²⁷.

A2. Repetitive TMS to target cognitive enhancement and resilience.

The proposed mechanism by which rTMS remediates depressive symptoms (i.e., up-regulating prefrontal control over dysregulated limbic activation) implies that rTMS should not only remediate depression, but should be a powerful transdiagnostic intervention for affective and cognitive dysregulation. In fact, high-frequency rTMS to left dIPFC is effective in reducing symptoms as far ranging as pain¹⁸, to

Taken together, it is not surprising that cognitive improvements have been reported as ancillary benefits to conventional²⁸⁻³⁰ as well as accelerated³¹ therapeutic rTMS for cognitively intact depressed patients. Accordingly, rTMS has also been shown to improve cognition as the primary outcome in studies of mild cognitive impairment³².

We propose that because rTMS to dIPFC is targeting cognitive neurocircuitry integral to adaptive cognitive functioning, that promoting neuroplasticity in this network with rTMS could be better optimized to both improve neurocognitive performance as well as enhance resilience to stress and neuropsychiatric dysfunction.

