To assess intervention acceptability, participants would be asked to rate pain and discomfort on a visual analog scale after each session⁸⁶. At the end of treatment participants would also complete a 5-item questionnaire about confidence in treatment procedures and mechanisms. To assess intervention safety, adverse events would be examined. To assess intervention feasibility, recruitment and retention rates would be examined. To assess intervention efficacy, neurocognitive, resilience, and symptom measures would be repeated after the last treatment session, and at 1 month post- treatment.

To assess neurocognitive performance, participants would complete the WinSCAT battery⁶⁰ (a computerized battery which takes about 10 minutes to complete and includes tests of reaction time, short term memory, and visual memory and is used by NASA to assess cognitive function in astronauts during International Space Station flights), the NIH Toolbox⁶² (a comprehensive set of neuro-behavioral measure that assess cognitive, emotional, sensory, and motor functions), as well as subtests from the Penn Computerized Neurocognitive Battery⁶¹. The battery includes well-validated computer- adaptations of neuropsychological tests (approximately 60 - 90 minutes total). Tasks assess domains including: information-processing speed, sustained attention/vigilance, verbal memory, working-memory capacity, cognitive flexibility, episodic memory, performance monitoring, resistance to interference, spatial memory, set shifting, inhibition/impulsivity, verbal learning, episodic memory, sensorimotor function and processing speed.

To assess resilience, stress, and affective function, participants would complete the Connor-Davidson Resilience Scale⁶³, a 25-item scale assessing hardiness, sense of control, adaptability,

stress endurance and self-confidence. The 17-item Hamilton Scale for Depression (HAM-D) The 10-item Perceived Stress Scale⁶⁴ would be completed to assess subjective stressors and their impact. The 99-item self-report Inventory of Depression and Anxiety Symptoms (IDAS-II)⁶⁵ would be completed as a broad measure of psychopathology and related functional impairment. The measure includes 18 non-overlapping factor-analytically-derived symptom subscales covering a wide range of psychopathology dimensions such as anxiety, depression, mania, insomnia, appetite).

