13.0 Risks to Subjects

Risks associated with TMS and MRI.

Challenges will include patient tolerability to TMS, the MRI scanner, and the study clinical and neurocognitive assessments. The primary safety concern, the same as that for conventional once-daily rTMS, is risk of seizure. However, all reported TMS-induced seizures during conventional or accelerated protocols have been self-limiting, and NONE required further intervention to stop the seizure; no post-seizure sequelae or recurrent seizures developed. Extensive precautions with regard to suicidal ideation/homicidal ideation risk will be followed.

Due to the novel nature of the proposed study, Table 4 is included to provide a representative range of the stimulation parameters and populations examined with accelerated rTMS. The dosing range of these studies covers the range proposed in this study. In these as well as other accelerated rTMS studies, the authors have demonstrated the safety, feasibility and acceptability of accelerated, high-dose studies of rTMS in neurologically intact samples. Of pertinence to the issue of safety as well as the conceptual model proposed here, Holtzheimer et al.⁸¹ showed reliably enhanced neuropsychological performance on the Repeatable Battery for the Assessment of Neuropsychological Status (RBANS) from baseline to six weeks after an accelerated, high-dose rTMS protocol in patients with major depression. Furthermore, Baeken et al.^{82,83} as well as Herremans et al.⁸⁴ and Williams et al.⁸⁵ additionally collected structural and functional imaging and demonstrated no adverse changes pre- to post-accelerated rTMS. Taken together, these studies demonstrate that the potential risks of accelerated rTMS are likely similar to conventional once-daily rTMS.

Table 4 . Representative accelerated rTMS studies for neuropsychiatric conditions.

Study	Total Pulses	Days	Total # Sessions	Stimulation Intensity	Disorder	Frequency	N
Holtzheimer et al. ⁸¹	15,000	2	15	100%	Major Depression	10 Hz; 5s train, 25s ITI	14
Baeken et al. ^{82,83}	31,200	4	20	110%	Major Depression	20 Hz; 1.9s train; 12s ITI	15
Herremans et al. ⁸⁴	31,200	3	15	110%	Alcohol Use Disorder	20 Hz; 1.9s train; 12s ITI	19
Desmyter et al. ⁹²	32,400	4	20	110%	Major Depression	54 bursts of three; 2s train; 8s ITI s	50
Duprat et al. ⁹³	32,400	4	20	110%	Major Depression	54 bursts of three; 2s train; 8s ITI s	50
[name] et al. ⁸⁶	54,000	3	9	120%	Suicidal ideation	10 Hz;	41

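### Arm 2's 80% power enters a baseline-to-follow-up change in depressed patients as the active-versus-sham difference in healthy adults, and is computed for a contrast other than the planned pre/post test

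*Combined protocol and SAP*

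**What the plan says.** In the Statistical Plan (section 10.0, Arm 2), the predicted effect comes from a cited accelerated rTMS study: a "reliable change of 5 standard units on the RBANS (SD=8.9"). The next sentence uses the same two numbers as a group comparison: "group sample sizes of 27 achieve 80% power to detect a difference of 5.000 (SD=8.9"). It assumes three measurements per participant under compound symmetry, and states that "the correlation between observations on the same subject is 0.300, and alpha level is 0.050". The target is "target completion reached with 30 participants each completing active and sham conditions (60 participants total").

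The same paragraph plans linear mixed-effects models that test whether pre-to-post change differs between active and sham.

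Section 13.0 describes the source result as enhanced RBANS performance "from baseline to six weeks after an accelerated, high-dose rTMS protocol in patients with major depression". Table 4 lists 14 patients for that study.

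Arm 2 takes its assessments from Arm 1 (section 9.0): "To assess neurocognitive performance, participants would complete the WinSCAT battery", the NIH Toolbox and subtests of the Penn battery. The RBANS is mentioned only in the power rationale and the risk section. Section 4.0 excludes anyone with a current psychiatric diagnosis.

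Sections 2.0 (A6) and 5.0 report that the sponsor approved combining studies 1 and 2 into Arm 4. Arm 2's design, recruitment target and power statement nevertheless remain in the current text.

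**The concern.** Two things separate the stated 80% from Arm 2's primary comparison.

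- **The input.** A change from baseline in treated patients equals an active-minus-sham difference only if sham does not change at all. Arm 2 repeats its cognitive tests before treatment, immediately after, and at 1, 2 and 6 months, so some practice gain in both groups is plausible. The plan deducts none. It also gives no reason why a value from depressed patients on the RBANS should carry over to healthy adults on a different composite, and no SD or correlation for that composite.
- **The contrast.** The calculation that returns 27 per group compares group means averaged over three measurements. The planned analysis tests a difference in change. At a correlation of 0.30 the two have very different variances.

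At stake is how Arm 2 would be read. A null result from a trial described as having 80% power looks like fair evidence against a worthwhile effect. It would be weaker evidence if power for the planned test was nearer one half.

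**Working it through.** **Inputs (section 10.0, Arm 2):** difference d = 5, SD = 8.9, m = 3 measurements, compound symmetry, ρ = 0.30, α = 0.05, 27 per group for 80% power, 30 per group planned. Sidedness is not stated. Nor is it stated whether 8.9 is the SD of a score or of a change; it is read as a score SD unless noted.

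**Power:** two-sided two-sample t-test, noncentral t with 2n − 2 degrees of freedom and noncentrality δ = d / (s·√(2/n)), where s is the SD of the contrast.

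**1. Reproducing the plan.** For the mean of three measurements, s = 8.9·√((1 + 2×0.3)/3) = 8.9·√0.5333 = 6.50. At n = 27, δ = 5/(6.50·√(2/27)) = 2.83 and power is 79.2% (80.7% by the normal approximation, which also returns n = 27). A one-sided test would need only 21 per group and does not match. At the planned n = 30, δ = 2.98 and power is 83.4%.

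**2. Same inputs, contrasts closer to the planned test, n = 30 per group.**

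| Contrast | s | δ | Power |
|---|---|---|---|
| Average of 3 measurements (the plan's figure) | 6.50 | 2.98 | 83% |
| One post visit minus baseline | 8.9·√(2×0.7) = 10.53 | 1.84 | 44% |
| Mean of two post visits minus baseline | 8.9·√(0.7×1.5) = 9.12 | 2.12 | 55% |
| One post visit adjusted for baseline | 8.9·√(1 − 0.3²) = 8.49 | 2.28 | 61% |
| Change score, if 8.9 is already the SD of change | 8.90 | 2.18 | 57% |

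No sham response is assumed here. For 80% power, the simple change contrast needs about 70 per group and the baseline-adjusted one about 46 (normal approximation).

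**3. Effect of the correlation.** A low ρ helps the average and hurts the change. At ρ = 0.5, 0.6 and 0.7 with n = 30, power for simple change is 57%, 67% and 79%; for the average it is 75%, 70% and 67%.

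**4. Allowing for sham or practice gain (assumed range; the documents give none).** For the time-averaged contrast (s = 6.50), n = 30:

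| Sham gain | Net difference | Power |
|---|---|---|
| 0 | 5 | 83% |
| 1 | 4 | 65% |
| 2 | 3 | 42% |
| 2.5 | 2.5 | 31% |

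**5. SD of the trial's own composite in RBANS-equivalent units (assumed, both directions).** For the time-averaged contrast with difference 5 and n = 30, SD 7, 8, 10 or 12 gives 96%, 90%, 74% or 58%.

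**The case against.** The strongest reply is that borrowing a standardised effect is ordinary planning when no direct data exist, and that the plan already words its power as conditional on a difference of 5 with SD 8.9. The arithmetic is correct, and 30 per group gives a small margin over 27. All of that stands. What is missing is any argument that 0.56 SD carries over, any allowance for sham gain, and a match between the calculation and the planned test.

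Two tempting arguments should not be used. One is that sham participants will also show recovery: they are healthy and have no depression to recover from, so only practice or expectancy gain applies. The other is that the remark in section 2.0 about "healthy individuals for whom neurocognitive performance has a more restricted range" shows that power is lower. That sentence goes on to report improved working memory after a single session, and a restricted range can shrink the SD as well as the effect. Its net direction is unknown, which is why step 5 runs both ways.

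It is also fair to say that Arm 2 may never run. Arm 4 randomises among ten active doses with no sham-only group, so this power statement does not apply to it. The statistical plan still points to a randomised controlled trial under Aim 2, so the statement is not void, but its practical weight depends on Arm 2's status.

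**Conclusion.** The concern holds. The 80% is arithmetically right for its inputs, but those inputs are a within-patient change on another test in another population, and the contrast is not the planned one. With the plan's own numbers and 30 per group, power is about 83% for the time-averaged difference, about 44% for simple post-minus-pre change and about 61% for one post visit adjusted for baseline. These three figures need no assumption about sham, but they do rest on 8.9 being the score SD and on ρ = 0.30.

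A reader might infer that Arm 2 is shown to be underpowered, or that 44% is its true power. The documents do not support that. They give no active-versus-sham difference, SD or correlation for the composite in healthy adults. A smaller SD would raise power, and ρ = 0.7 alone would bring simple change back to about 79%. The supported conclusion is that Arm 2's power for its primary comparison is not established by the plan.

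**What to change.** If Arm 2 is still to be run, say so, and revise its power paragraph as follows:

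- State power for the planned active-minus-sham change in the neurocognitive composite, naming the visits and whether baseline is an outcome or a covariate.
- Label 5/8.9 = 0.56 SD as a borrowed standardised assumption, and say whether 8.9 is a score SD or a change SD.
- Give a sensitivity range for the net difference, SD and correlation, with the SD varied in both directions.
- Before Arm 2 starts, replace the SD and correlation with estimates from whatever Arm 1 and Arm 4 composite data are then available; those arms share Arm 2's eligibility criteria and cognitive assessments. Report the resulting power or detectable difference.

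If Arm 2 will not be run, mark its power statement as no longer applicable.

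The cost is a paragraph and one calculation. The stated power may be less favourable; the restatement itself adds no participants.
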